## 4. SELECTION AND ENROLLMENT OF PARTICIPANTS

### 4.1 Inclusion and Exclusion Criteria

All TACT2 participants must meet of the following inclusion criteria shown in Table 2.

Potential TACT2 participants meeting any of the exclusion criteria in Table 2 will be excluded from study participation.

**Table 2:** Inclusion and exclusion criteria

INCLUSION CRITERIA (all must be present)	EXCLUSION CRITERIA (none may be present)

1. Age <math>\geq</math> 50 years
 
2. History of diabetes, defined as medical record evidence or patient report of currently using insulin or oral hypoglycemic agents, or with a history of fasting blood glucose measurement of 126 mg/dL or higher, or a history of HbA1c of 6.5% or higher.
 
3. History of myocardial infarction based on the Universal Definition of MI.
 
 
a. When information about the MI hospitalization is available, all MI types except Type 2 qualify for study entry.
 
b. When information about the MI hospitalization is not available, a wall motion abnormality on imaging or a perfusion defect on scan that corresponds to a coronary distribution, whether or not accompanied by pathological Q waves in the appropriate distribution, will qualify the patient for study entry. This criterion requires a call to the CCC for case review.
 
	
1. Baseline serum creatinine <math>>2.0</math> mg/dL.
 
2. HbA1C <math>>11\%</math>.
 
3. Myocardial infarction within 6 weeks of randomization.
 
4. History of allergic reactions to EDTA or any other components of the chelation solution, including heparin. Site personnel are to call the CCC to discuss heparin allergy.
 
5. Coronary or peripheral arterial revascularization procedure performed within the last 6 months.
 
6. Planned revascularization procedure in the 6 months following enrollment.
 
7. Heart failure hospitalization within 6 months prior to enrollment or in clinical heart failure at the time of proposed enrollment (such as NYHA Class 3 dyspnea + rales <math>></math>basilar, and additional signs of fluid overload). Such patients may be treated with diuretics and enrolled when stable.
 
8. Poor or no venous access in the upper extremities.
 
9. a. Prior intravenous chelation therapy consisting of <math>> 1</math> infusion within 5 years; if only 1 infusion took place, patient cannot be enrolled for at least 12 months after said infusion. b. Oral chelation therapy with an approved oral chelating agent within 2 years.
 
10. Prior participation in TACT.
 
11. Baseline platelet count <math><100,000</math>.
 
12. History of cigarette smoking within the last 3 months.
 
13. ALT or AST <math>> 2.0</math> times the upper limit of normal.
 
14. Wilson's disease, hemochromatosis, or parathyroid disease.
 
15. Any medical condition including a current diagnosis of cancer (except non-melanoma skin cancer) that will limit patient survival over the duration of the trial.


	
16. Any factor that suggests that the potential participant will not be able to adhere to the protocol.
 
17. Women of child-bearing potential including those with plans for post-menopausal in vitro fertilization or other reproductive technology.

--	--

## 4.2 Study Enrollment Procedures

TACT2 will enroll a population of stable, post-MI diabetic patients. The majority of patients, therefore, will be approached in the outpatient area, including:

- i. Cardiology practices of investigators, colleagues, or referral sources
- ii. Endocrinology practices of investigators, colleagues, or referral sources
- iii. Cardiac rehabilitation services (particularly in Canada)
- iv. Potential participants contacting clinical sites in response to IRB-approved advertisements
- v. Potential participants contacting clinical sites as a result of interviews, lectures, and social media

### Enrollment of Women and Racial and Ethnic Minorities

The TACT2 investigators are committed to recruitment of a representative sample of women and minority subjects as required by NIH, and we understand that failure to do so will decrease the validity and generalizability of study results. TACT2 is well positioned to achieve its goals of enrolling subjects representative of the US population. We are selecting patients for study that are age 50 or older, which has the corollary benefit of achieving a more equivalent distribution of men and women for whom coronary artery disease (CAD) is the leading cause of death. Moreover, we anticipate randomizing patients who predominantly have Type 2 diabetes (T2D). Compared with non-Hispanic whites, the risk of diagnosed diabetes is 70% higher among African Americans and 80% higher among Hispanics, which also has the corollary effect of helping us to achieve a sample that is sufficiently representative of these minority populations. TACT2 will target enrollment of at least 40% women and 18% minority subjects, which is in line with the demographics of prevalent myocardial infarction (MI) in the US population and the realities of enrolling women and minorities, as shown by our review of the literature.

### Targeted Enrollment of Women

We are committed to enrolling sufficient numbers of women so that the results of TACT2, if positive, will be plausibly applicable to women. The target proportion of women to be enrolled in TACT2 is lower than the overall proportion of women in estimates from the 2010 US Census (51%), but it is consistent with current estimates of the proportion of prevalent MI among women, especially those with diabetes. Based upon cardiovascular disease (CVD) surveillance from 1994-1997 in the NHLBI Atherosclerosis Risk in Communities (ARIC) Study, one of the largest NHLBI population cohort studies and CVD surveillance programs, 32% (n=4,253) of 13,068 hospitalizations for MI occurred in women. More recent data from the 2014 Heart

Disease and Stroke Statistics update from the American Heart Association (AHA) reported a similar proportion of prevalent MI in women (34%). Gore et al., based on the National Registry of Myocardial Infarction (NRMI), reported that 44.8% of incident MIs in diabetics occurred in women, with an 8.4% in-hospital mortality that was slightly higher than that of men. Perhaps more to the point of the attainable, the FREEDOM Trial reported its results in 2012. This was an NIH study of revascularization strategies in diabetic patients with multivessel coronary disease. There were 1900 patients enrolled, and 29% were women (Similar to ARIC, above). The TACT2 leadership has carefully considered the population goal as reported by Gore, and the attainable goal from FREEDOM. While we believe we can improve on FREEDOM, we do not realistically believe we can enroll a population fully reflective of Gore et al. Thus, our goal of enrolling at least 40% women in the TACT2 trial is justified.

### **Targeted Enrollment of Minorities**

Our goal for enrollment of minorities is more reflective of the Gore data, which reported 18.2% minorities in the NRMI diabetes dataset. This proportion included 9% black and 3.4% Hispanics. Overall, the TACT2 enrollment target of 18% for minority patients is justified based on these data and is in accord with published data on the proportion of minority patients with prevalent MI used by the AHA, ACC-NCDR and VAMC.

### **Additional Strategies to Enroll and Retain Women and Minorities**

Current informal surveys of patients undergoing chelation have already led to suggestions for sites to consider infusions of multiple patients simultaneously in a socially compatible group setting, to consider gender-based infusion groups, particularly for women patients, and to consider extended hours or weekend infusions.

Strategies will be added or modified throughout the study, as formal surveys of patients are performed, and sites apply or discard different approaches. These plans will form part of a living document external to this Protocol, entitled “Plans to Identify, Recruit, Enroll, and Retain Women & Minorities.”

## **5. STUDY INTERVENTIONS**

### **5.1 Interventions, Administration, and Duration**

**Chelation/placebo infusions:** The active infusion contains up to 3 g of Na2EDTA adjusted based on eGFR, 2 g of magnesium chloride, 100 mg of procaine HCL, 2500 U of heparin, 7 g of ascorbate, 2 mEq KCl, 840 mg sodium bicarbonate, 250 mg pantothenic acid, 100 mg of thiamine, 100 mg of pyridoxine, and sterile water to complete 500 mL. Placebo infusions consist of 500 ml normal saline with 1.2% dextrose. Infusions are administered weekly for 40 weeks. More details can be found in the Manual of Procedures (MOP).

The dose of edetate disodium in the infusion solution will be adjusted based on estimated creatinine clearance and ideal body weight (IBW), but in no case will ever exceed 3 grams per infusion (3000mg):

$$\text{EDTA dose (mg)} = [50\text{mg} \times (\text{IBW} \times 1.33) \times \text{min (100, creatinine clearance)}] \div 100$$

The IBW is calculated based on the Devine formula:

- For men the weight is computed as 50 kg plus 2.3 kg for each inch of height over 5 feet (or 60 inches).
- For women the weight is computed as 45.5 kg plus 2.3 kg for each inch of height over 5 feet (or 60 inches).
- Actual body weight is used whenever it is less than computed ideal body weight.

**Correction for creatinine clearance should only be done if creatinine clearance is less than 100.**

Creatinine clearance will be computed by using a modified version of the Cockcroft-Gault equation:

$$\text{Creatinine Clearance (ml/min)} = \frac{(140 - \text{age}) \times (\text{IBW} \times 1.33)}{(72 \times \text{Cr})}$$

Creatinine Clearance = computed renal glomerular filtration rate in ml/min

Age = patient's age

IBW = computed weight in Kg

Cr = serum creatinine in mg/dL

For women, multiply the above result by 0.85

EDTA dose is automatically adjusted by the electronic data capture system based on the most recently calculated creatinine clearance value. If a prescription change for EDTA is required, the pharmacy is automatically notified by the electronic data capture system. The pharmacy will adjust the EDTA for the patient's next scheduled infusion.

Serum calcium is corrected by albumin level to generate a corrected calcium value that is an estimation of ionized calcium^45 as follows:

$$\text{corrected calcium} = \text{serum calcium} + (0.8 \times [\text{normal serum albumin} - \text{patient's albumin}])$$

calcium= mg/dL

albumin= g/dL

- When corrected calcium is greater than 8.5 mg/100mL, the infusion is administered over 3 hours.
- When corrected calcium is between 8 and 8.5, the infusion is administered over 4 hours.
- When corrected calcium is less than 8, the next infusion is not administered and serum calcium is rechecked at least 1 week later. When corrected calcium is within acceptable range, infusions continue. This usually leads to a 2 week delay in infusions.

**OMVM/placebo:** The OMVM consists of 3 caplets, twice daily for a total intake of vitamin A 25000 IU, vitamin C 1200 mg, vitamin D3 100 IU, vitamin E 400 IU, vitamin K1 60 µg, thiamin 100 mg, niacin 200 mg, vitamin B6 50 mg, folate 800 µg, vitamin B12 100 µg, biotin 300 µg, pantothenic acid 400 mg, calcium 500 mg, iodine 150 µg, magnesium 500 mg, zinc 20 mg, selenium 200 µg, copper 2 mg, manganese 20 mg, chromium 200 µg, molybdenum 150 µg, potassium 99 mg, choline 150 mg, inositol 50 mg, para-aminobenzoic acid 50 mg, boron 2 mg, vanadium 35 µg, citrus bioflavonoids 100 mg. Placebo caplets consist of microcrystalline cellulose, stearic acid, croscarmellose sodium, silica and magnesium stearate. OPADRY® II complete film white coating, magnesium stearate and vanilla flavor are used to coat both active and placebo pills. These caplets are taken for the entire duration of the study.

**Low-dose vitamins:** The low-dose supplements are taken by all patients to prevent any deficiency syndromes from chelation of essential minerals or vitamins. They consist of: vitamin B6, chromium, copper, manganese, and zinc. As was done in TACT, all patients will receive a low-dose regimen consisting of a single pill to be taken during the infusion regimen, stopping at 1 year at the latest. The low-dose regimen consists of: vitamin B6 25 mg, zinc 25 mg, copper 2 mg, manganese 15 mg, and chromium 50 µg.

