The biological effects of EDTA are due to the formation of chelates with divalent and trivalent metals. The stability of the metal-EDTA complex is directly related to its pH – the higher the pH, the more stable the chelate. Intravenous infusions of edetate disodium result in the chelation of ionized calcium. Transient but mild reduction of serum calcium can be observed following the slow intravenous infusion of EDTA, and was observed in TACT (below). 1gm of EDTA can effectively bind approximately 120 mg of calcium. Among metals normally found as trace metals and metals present pathologically, EDTA has been demonstrated to bind and promote the excretion of cadmium, lead, zinc, copper, iron, manganese, and vanadium. Virtually all of the metals chelated by EDTA are excreted in the urine within 24 hours. In the case of calcium, 28% is excreted during the infusion, 60% in the 6 hours following the infusion, and the remainder between 6 and 12 hours after. Among the essential metals chelated by disodium EDTA are copper and iron. Both of these metals have an important role in oxidative state and generally exist in an intracellular compartment or protein-bound. However, there is an important, non-protein bound component that may be chelated by EDTA salts. EDTA salts may promote the excretion of up to 10 mg/day of iron and increase urinary copper by almost 140%. The oral supplement regimen in TACT2 repletes copper. Iron was not substantially diminished by EDTA in TACT, and will be measured during the TACT2 infusion regimen.

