### Infusion Schedule

Infusions will be administered on a weekly basis for 40 weeks through a peripheral intravenous line over at least 3 hours. Due to vacations, travels, weather, and illness,

the infusion regimen can be extended but is expected to be completed by 1 year. Clinical sites, however, will be instructed that if a patient has not completed the infusions by 1 year, they should continue trying to get the patient to clinic until the 40th infusion is complete. The total number of infusions is key, not the weekly schedule on 1-year completion. **The overall goal of the treatment schedule is to deliver all 40 infusions; no matter how long it takes.** The DCRI Call Center will follow patients for clinical events, but not for infusion scheduling or other site-centered events beginning 6 and 12 months after randomization, and at 4 month intervals subsequently until the study ends.

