## **5.4 Adherence Assessment**

Assessing infusion adherence: the site coordinators will enter in the eCRF if the infusion was completed. In cases where the infusion was started and not completed, the site coordinator will estimate whether more or less than ½ of the infusion was infused.

Assessing OMVM adherence: During the study, OMVM will be delivered every 4 months in bottles. Each dose pack will have 6 OMVM/placebo pills inside. Each bottle will have 30 dose packs. At designated intervals during the study, the patient's compliance will be assessed.

Assessing low-dose vitamin adherence: The low-dose regimen is to be taken during the infusion phase only. The subjects should take one low-dose pill daily. When patients are non-compliant with this regimen they will be advised by site staff regarding its importance.

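### The low-dose mineral pill stops at 1 year but chelation infusions may continue beyond it, so late-infused patients on active chelation plus placebo OMVM lose the planned repletion

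*Protocol*

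**What the plan says.** Protocol Section 5.1 (Low-dose vitamins) gives all patients a low-dose supplement, and states its purpose as "to prevent any deficiency syndromes from chelation of essential minerals or vitamins". It is one pill, taken while the infusions are being given and "stopping at 1 year at the latest". Section 5.4 adds: "The low-dose regimen is to be taken during the infusion phase only".

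Section 5.2 (Infusion Schedule) expects the course to be finished within 1 year. It then says what to do when it is not: sites keep trying to bring the patient in until the 40th infusion has been given. "The overall goal of the treatment schedule is to deliver all 40 infusions; no matter how long it takes".

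Section 2.2 (EDTA Pharmacology) says that "EDTA has been demonstrated to bind and promote the excretion of cadmium, lead, zinc, copper, iron, manganese, and vanadium", and also that "The oral supplement regimen in TACT2 repletes copper".

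**The concern.** A site can follow every one of these rules, and in doing so it withdraws the stated protection while active infusions go on. The pill has a calendar limit; the infusions have none.

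What is at stake is patient safety, by the protocol's own reasoning: a supplement judged necessary because of chelation is removed while chelation continues. The scheduled laboratory tests in Section 6.1 include no zinc, copper, manganese or chromium, so a deficiency during late infusions would not show up there. Under Section 7.1 the last blood count falls at infusion 40 or at 1 year, whichever is earlier, so for a late-infused patient it comes before the gap. Section 7.4 does not collect non-serious adverse events on the case report form.

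**Working it through.** The plan gives no figure on this point to reproduce. The check has two parts: which patients lose cover, and for how long.

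**Which patients.** Sources of the five pill components, from Protocol Section 5.1:

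| Component | Low-dose pill | Active OMVM, daily total | Placebo OMVM | Active infusion |
|---|---|---|---|---|
| Vitamin B6 | 25 mg | 50 mg | none | 100 mg each |
| Zinc | 25 mg | 20 mg | none | none listed |
| Copper | 2 mg | 2 mg | none | none listed |
| Manganese | 15 mg | 20 mg | none | none listed |
| Chromium | 50 µg | 200 µg | none | none listed |

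- Active OMVM runs for the whole study, so those patients keep all five components when the pill stops.
- Placebo-infusion patients are not chelated.
- On active chelation plus placebo OMVM, each infusion still brings "100 mg of pyridoxine", so B6 is covered. The four minerals are not.
- Section 5.3.2 prohibits over-the-counter vitamins that share components with the study vitamins, apart from a waiver granted case by case, so patients are not expected to make up the loss themselves.
- Section 2.2 names zinc, copper and manganese among the metals EDTA removes. It does not name chromium.

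The gap is therefore confined to active chelation plus placebo OMVM, about 250 of 1000 patients (Précis), and within that arm to those still being infused after 1 year.

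**How long.** Assumptions: 1 year is day 365 from randomization, and the infusions are evenly spaced. Infusion number k + 1, for k = 0 to 39, falls on day s + d × k, where s is the day of the first infusion and d the spacing in days. Section 6.2 asks for the first infusion within 2 weeks of randomization, so s is taken as 0 or 14.

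- Strictly weekly (d = 7): the last infusion falls on day 14 + 39 × 7 = 287, or day 273 if s = 0. That leaves 365 − 287 = 78 days of slack (about 11 weeks), or 92 days (about 13 weeks).
- Largest mean spacing that still finishes by day 365: (365 − 14) / 39 = 9.0 days, or 365 / 39 = 9.36 days if s = 0.
- Section 5.1 says that a hold for low calcium usually costs 2 weeks. At 14 days each, 78 / 14 = 5.6 and 92 / 14 = 6.6, so six or seven such holds would use up the slack without any other delay.

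The documents give no distribution of spacing, so the values of d below are assumed:

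| d (days) | s | Infusions after day 365 | Day of last infusion | Days from day 365 to last infusion |
|---|---|---|---|---|
| 10 | 14 | 4 | 404 | 39 |
| 12 | 14 | 10 | 482 | 117 |
| 14 | 14 | 14 | 560 | 195 |
| 10 | 0 | 3 | 390 | 25 |
| 12 | 0 | 9 | 468 | 103 |
| 14 | 0 | 13 | 546 | 181 |

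For example, with d = 10 and s = 14, a day beyond 365 needs k > 35.1, so k = 36 to 39, which is 4 infusions.

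**The case against.** The strongest reply is that the cap is a deliberate choice carried over from TACT, that completion within 1 year is the expectation, and that slow patients have already taken more supplement per infusion. The last point is right as arithmetic. Counting pills from a first infusion on day 14, a strictly weekly patient takes about 273 pills for 40 infusions, or 6.8 each. A late patient has taken about 351 by day 365, which is 351 / 40 = 8.8 each even when spread over all 40. Late infusions are also further apart. This tempers the likely size of any deficit. It does not supply minerals during the late infusions, which at 14-day spacing run for 195 days after the last pill.

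The copper sentence in Section 2.2 may refer to OMVM and not to the low-dose pill. That stands as an ambiguity, but it does not help: this arm takes placebo OMVM, so on either reading it has no protocol copper once the pill stops. The purpose sentence in Section 5.1 carries the point on its own.

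Section 1.2 mentions a wider multi-element metals panel, and samples are taken at infusion 40, which for a late patient falls after the cap. The panel's elements are not listed, its use is prognostic research, and Section 6.1.2 describes intermittent batch transfer. It is not shown to be safety monitoring.

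Three further limits stand. The wording in Section 5.4 restricts the pill to the infusion phase but does not promise cover throughout it. The number of patients infused late is unknown and could be small. The Manual of Procedures, which is not among the documents, may set a different stop.

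**Conclusion.** The concern holds. The 1-year cap on the pill and the open-ended infusion rule leave late-infused patients on active chelation plus placebo OMVM without the zinc, copper, manganese and chromium that the protocol gives because of chelation. The ceiling is about 250 patients. The true number is not in the documents, and patients who died, withdrew or stopped infusions do not count towards it. Under the assumed spacings of 10 to 14 days, an affected patient would receive 3 to 14 infusions after the pill has stopped. The documents contain no deficiency data, so the clinical risk cannot be sized. The trial's endpoints, power and type I error do not depend on this point. It is worth correcting because it concerns patient safety and the correction is cheap, not because it threatens the result.

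**What to change.** In Protocol Section 5.1, replace "stopping at 1 year at the latest" with: stopping at the patient's last infusion. This is consistent with Section 5.4. If the Manual of Procedures already sets a later stop, state that stop in Section 5.1.

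The cost is one line of text and some extra supply of an existing pill. At one a day, that is about 39 to 195 more per late-infused patient with a day-14 start, or 25 to 181 with a day-0 start. All arms take the pill, so extending it for every patient still being infused leaves blinding unaffected. The change was still relevant when the current version was issued: the protocol is dated May 2021, and SAP Appendix I plans the last randomized patient's infusions to end in December 2021. Those dates show that infusions were still to come under this text; they do not show that any fell after 1 year.

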## 5.2 Handling of Study Interventions

### Infusion Encounter

The clinical unit will administer infusions. Infusions will be received in a refrigerated individual overnight mailer that will contain an IV bag and 2 syringes, each labeled for the individual patient. Typically, the infusion kit is received the day before the infusion is scheduled, and is good for 72 hours if unmixed. Once mixed, the refrigerated infusion will be good for 24 hours only. The specifics will be covered in detail in the MOP.

Each infusion encounter will be preceded by a brief interval history with specific emphasis on cardiac symptoms and clinical events, including hospitalizations. Vital signs will be measured before and after the infusion prior to discharge from the infusion site. A brief cardiopulmonary exam will be recorded at screening and at the end of each infusion. If there is weight gain of 3 lbs or more since the last infusion, or 5 lbs or more since the screening evaluation, the patient will be evaluated for heart failure. A trained study coordinator or infusion nurse may perform this examination. If there is heart failure, the infusion will be delayed until the patient is treated. Symptoms occurring during the infusions will be elicited and recorded on the eCRF. Patients will take their diabetes medications as scheduled unless a blood draw is scheduled. In that case, patients will arrive after an overnight fast and the diabetes medications will be held until the morning blood draw prior to the beginning of the infusion. Patients may consume food and drink during the infusion.

